6.3. Follow-Up Period

All subjects will be followed for 28 days after the last dose of IP for AE reporting, as well as SAEs that will be followed until the last study visit and made known to the investigator at any time thereafter that are suspected of being related to IP, as described in Section 11.1.

The Follow-up Period will take place from Visit 10 through Visit 13 and include Early Termination. Visits should occur on the day specified ± 3 days or ± 7 days as specified in the Table of Events (Table 1).

All other procedures (as discussed in Section 6.1 and Section 6.2) will be conducted as per the Table of Events (Table 1).

6.4. Efficacy Procedures

The following efficacy assessments will be performed as outlined in the Table of Events (Table 1).

Epidermal Nerve Fiber Density (ENFD): This assessment relies on an immunohistochemical localization of a neural antigen within axons. Histological specimens will consist of serial 3mm thickness punch biopsies of the epidermis taken bilaterally at the lateral aspect of the distal legs. To quantify ENFD (fibers/mm of epidermis), the pathologist manually counts the number of

epidermal nerve fibers in 3 to 5 sections and divides the value by the lengths of the epidermal specimens in millimeters. In addition, a quantification of the autonomic sudomotor (sympathetic cholinergic) and pilomotor (sympathetic adrenergic) nerve fibers will be conducted within the same biopsy.

Histology of Immune Cells: Two skin biopsies will be taken from the volar aspect of the forearm. The first biopsy will be used for histology analysis to evaluate the inflammatory response by assessing inflammatory cell infiltration. The second biopsy will be used to perform mRNA / protein analysis.

Circulating Blood Biomarkers: Blood collected to be used for biomarker analysis will include whole blood collection for blood immune biomarkers and red blood cell (RBC)-lysed peripheral blood mononuclear cell (PBMC) sample for the chip cytometry immune phenotyping assay*.

* These assessments for RBC-lysed peripheral blood mononuclear cell (PBMC) by the chip cytometry assay will only be performed at selected sites.

Hyperspectral Imaging *: Hyperspectral imaging (HIS) obtains multiple images at discrete wavelengths, providing a diffuse reflectance spectrum of each pixel in the image. The system uses wavelengths between 500 and 600 nanometers which serve to obtain oxy- and deoxy-hemoglobin absorption peaks. Tissue oxygenation images or "maps" are then constructed from oxy- and deoxy-hemoglobin values determined from each pixel in the image. HSI will be measured in both lower limbs.

*This procedure will be measured only if it is available for this study protocol at the participating site.

6-item Neuropathy Total Symptom Score (NTSS-6): The NTSS-6 questionnaire is used to evaluate the frequency and intensity of neuropathy sensory symptoms identified by subjects with DPN (ie, numbness and/or insensitivity, prickling, and/or tingling; burning pain; aching pain and/or tightness, sharp shooting lancinating pain and allodynia and/or hyperalgesia). Symptoms are graded based on the experience of the subject during the past 24 hours. Each symptom question can be assigned a maximum score of 3.66 points. The symptom scores are summed, and the total score can range from 0 points to 21.96 points. A higher score indicates greater disability.

Neurological Impairment Score of the Lower Limb (NIS-LL): The NIS-LL is an assessment tool composed of a sensory subscore (which evaluates sensory perceptions to touch, prickling pain, vibration, joint position, and to 1 gram and 10 gram monofilaments), and a motor subscore (which evaluates muscle strength, muscle wasting, and deep tendon reflexes) in the lower limbs. The scale is additive for all deficits and is applied in a bilateral manner for each modality tested. The subscores are totaled and can range from 0 points (normal neurological function) to 88 points (absence of all motor, sensory, and reflex activity). An increase of 2 points is clinically significant.

Utah Early Neuropathy Scale (UENS): The UENS uses a physical examination specific to early sensory predominant polyneuropathy which emphasizes severity and spatial distribution of sharp sensory loss in the foot and leg. The total score can range from 0 to 42. A higher score indicates greater disability.

Electro physiologic Nerve Conduction Studies: Nerve conduction studies allow for the quantification of the conduction amplitude, velocity, and latency of the tibial and peroneal nerves, and the amplitude and latency of the sural nerve. Reduction of amplitudes of recorded responses generally indicates a loss of axons. Nerve conduction will be measured in both lower limbs.

Quantitative Sudomotor Axon Reflex Testing (QSART): QSART is a measurement of autonomic involvement by evaluating postganglionic sudomotor function deficits in the foot, distal leg, and distal thigh.

Patient Global Impression of Change in Neuropathy (PGICN): The PGICN is a subject's self assessment to describe and change in symptoms of neuropathy such as pain, tingling, or numbress.

Health-Related Quality of Life (QOL) as measured by the Norfolk QOL-DN: The Norfolk QOL-DN is composed of 5 domains (physical functioning/large fiber neuropathy, activities of daily living, symptoms, small fiber neuropathy, and autonomic nerve function) encompassing 35 scored questions related to subjects' neuropathy signs and symptoms, as well as to the impact of DPN on subjects' activities of daily life. The total score can range from -2 to 138. A higher score indicates higher disability.

Vascular Reactivity Measurements*: Vascular reactivity will be measured by using Laser Doppler Iontophoresis and Nerve Axon Reflex measurements in both lower limbs. By applying acetylcholine chloride, the endothelium-dependent vasodilatation may be measured. The MIC1 iontophoresis system will be used in this study. Specifically, a small quantity (<1 ml) of 1% acetylcholine chloride solution will be used on the forearm of the participating subjects; subsequently a constant current of 200 microampere will be applied for 60 seconds achieving a dose of 6 mC.cm⁻². The single spot reaction will be measured by Laser Doppler Flowmetry using a DRT4 Laser Doppler Blood Flow Monitor.

The Nerve Axon Reflex measurement will be performed at the foot level by using a single point Laser Probe during the acetylcholine iontophoresis. The single spot reaction will be measured by Laser Doppler Flowmetry using a DRT4 Laser Doppler Blood Flow Monitor. The probe will be attached to the center of the iontophoresis chamber. As the probe is not in direct contact with the foot, it will only measure the nerve axon-related vasodilation. The results are expressed as percentage of increase over the baseline blood flow.

*This procedure will be measured only if it is available for this study protocol at the participating site.

6.5. Safety

Safety will be assessed by an ongoing review of clinical laboratory tests (hematology, serum chemistry, coagulation, pregnancy, urinalysis, physical examination results, vital sign measurements, 12-lead ECG at screening only, weight, use of concomitant medications/procedures, and the incidence and severity of injection site and injection-related reactions (including tryptase and histamine) and treatment-emergent AEs.

6.5.1. External Data Monitoring Committee

An external unblinded DMC will monitor safety and efficacy information to ensure subject safety in accordance with a separate charter. The external DMC will be comprised of members who are not involved in the day-to-day activities of the PDA-002 DPN study team. Data review packets will be forwarded to the DMC members for review at least 7 days prior to each scheduled DMC teleconference/meeting. Data will be current through 14 days prior to each scheduled DMC teleconference/meeting.

The external DMC will be convened to assess the benefit risk of PDA-002 when approximately 25% and 50% of subjects complete the Month 3 (Visit 6) assessment. Study enrollment will be ongoing during these scheduled reviews.

The external DMC chairman will be notified if an AE of medical interest should occur and will determine if a full DMC will need to be conveyed. During any period of deliberation by the external DMC on an AE of medical interest, a temporary hold on enrollment of new subjects will be instituted. The AEs of medical interest that would trigger this process are:

- Identification of 1 or more subjects within a dosing treatment arm with \geq Grade 3 allergic reaction that is suspected to be related to the IP.
- Identification of 1 or more subjects experiencing a suspected unexpected, treatmentrelated SAE (SUSARs) within 14 days following the initial dose of the IP suspected unexpected serious adverse reactions.
- Identification of 1 or more subjects with a new malignancy.

The sponsor will take appropriate action based upon the external DMC recommendation and this will be communicated to the investigators. The investigators will be responsible for notifying their Institutional Review Boards (IRBs). The external DMC will evaluate on an ongoing basis all available safety data, in particular all SAEs and their potential relationship to PDA-002. The external DMC may recommend modifications to enrollment or to the study design in order to ensure subject safety. Further explanation of the roles and responsibilities of the external DMC will be outlined in the external DMC charter.

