^d Adverse events will be followed for 28 days after the last dose of IP. SAEs will be followed until the last study visit.

^e Prior to injection on Days 1, 29 and 57.

^f If performed within 28 days of signing the informed consent it does not need to be repeated.

6. **PROCEDURES**

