8.2. Treatment Administration and Schedule

Investigational product (IP) will be administered on Study Days 1, 29 and 57. Thawing of the IP should not begin until it is confirmed that the subject meets the inclusion/exclusion criteria. Investigational product thawing will be performed by qualified site personnel according to the instructions in Appendix E. Three 3 mL syringes will each be filled with 1.5 mL of IP, and then capped. Syringes will be masked to preserve blinding, and transferred to the personnel administering the injections.

Subjects will receive IP administered as fifteen 0.30 mL injections (approximately 4.5 mL total) in one leg. The target region is suggested to be below the knee and above the ankle. Injections are suggested to be at least 1 cm apart horizontally and laterally and at a depth of approximately 1 to 4 cm. It is suggested that they be administered in a pattern of 3 x 5 injections around the leg, and injections should not be near a blood vessel. The administrator will be blinded to treatment.

PDA-002 is not intended for intravenous administration. When the injection is given, the syringe should be aspirated to avoid inadvertent venous administration. If any blood is aspirated into the syringe, the needle is to be pulled out a little, and the syringe re-aspirated. If no blood is seen, the IP may be injected.

Vital signs (including heart rate, respiration, blood pressure, body temperature) will be monitored prior to starting the injections and at 1 and 2 hours (\pm 15 minutes) after completion of

the injections. Blood samples for tryptase and histamine, coagulation assessments, and exploratory biomarkers will be collected as indicated in the Table of Events (Table 1).

The investigational centers must also offer appropriate supplemental services that support clinical care to ensure that the protocol specified IP administration and monitoring will be followed.

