11.6. Expedited Reporting of Adverse Events

For the purpose of regulatory reporting, Celgene Drug Safety will determine the expectedness of events suspected of being related to PDA-002 based on the Investigator Brochure.

In the United States, all suspected unexpected serious adverse reactions (SUSARs) will be reported in an expedited manner in accordance with 21 CFR 312.32.

Celgene or its authorized representative shall notify the Investigator of the following information.

- Any AE suspected of being related to the use of IP in this study or in other studies that is both serious and unexpected (ie, SUSAR);
- Any finding from tests in laboratory animals that suggests a significant risk for human subjects including reports of mutagenicity, teratogenicity, or carcinogenicity.

Where required by local legislation, the Investigator shall notify his/her IRB/EC promptly of these new serious and unexpected AE(s) or significant risks to subjects.

The Investigator must keep copies of all pertinent safety information on file including correspondence with Celgene and the IRB/EC. (See Section 15.3 for record retention information).

Celgene Drug Safety Contact Information:

For Celgene Drug Safety contact information, please refer to the Serious Adverse Event Report Form Completion Guidelines or to the Pregnancy Report Form Completion Guidelines.

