12. DISCONTINUATIONS

12.1. Treatment Discontinuation

12.1.1. Events Leading to Suspension of Enrollment Pending DMC Evaluation

The following events in any subject will trigger a suspension of additional enrollment pending an evaluation by the Data monitoring Committee (DMC) of the event at an ad hoc meeting. Should such an event occur, the DMC will review the available data from the subject's history and the event itself as well as available data on all other previously treated subjects. The committee will recommend if it is appropriate to resume enrollment without study modifications, to resume enrollment with study modifications or to permanently discontinue further enrollment into the study. Operational details are specified in the DMC Charter.

- Identification of 1 or more subjects within a dosing treatment arm with ≥ Grade 3 allergic reaction that is suspected to be related to the IP.
- Identification of 1 or more subjects experiencing a suspected unexpected, treatmentrelated SAE (SUSARs) within 14 days following the initial dose of the IP suspected unexpected serious adverse reactions.
- Identification of 1 or more subjects with a new malignancy.

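### The SUSAR trigger for suspending enrolment is tied to the first dose, so other SUSARs after dose 2 or 3 bring no automatic pause

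*Combined protocol and SAP*

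**What the plan says.** Sections 6.5.1 and 12.1.1 carry the same list of three triggers: a Grade 3 or higher allergic reaction suspected to be related to the product, a SUSAR "within 14 days following the initial dose of the IP", and a new malignancy. Only the SUSAR trigger has a time limit, and only it refers to the first dose.

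The two sections attach different consequences to the list. Section 12.1.1 is automatic: "The following events in any subject will trigger a suspension of additional enrollment pending an evaluation" by the DMC at an ad hoc meeting. Under 6.5.1 the DMC chairman is notified and "will determine if a full DMC will need to be conveyed", with enrolment held while the committee deliberates.

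On dosing, section 8.2 states: "Investigational product (IP) will be administered on Study Days 1, 29 and 57". On enrolment, 6.5.1 plans DMC reviews when about 25% and 50% of subjects have completed Month 3, and adds: "Study enrollment will be ongoing during these scheduled reviews".

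Other safeguards apply whichever dose came last. Section 6.5.1 has the DMC evaluate all safety data, serious adverse events in particular, on an ongoing basis, and states: "The external DMC may recommend modifications to enrollment or to the study design in order to ensure subject safety". Section 4.1 allows ad hoc reviews if needed. Under 11.6, SUSARs in the United States "will be reported in an expedited manner in accordance with 21 CFR 312.32". Footnote d of the Table of Events states: "SAEs will be followed until the last study visit".

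**The concern.** The treatment is a three-dose course, but the SUSAR trigger stops before the second dose. The same reaction 10 days after dose 1 and 10 days after dose 2 would be handled differently under 12.1.1: the first suspends enrolment, the second does not. The protocol gives no reason for the difference.

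Elsewhere the protocol treats risk as recurring with each dose. The stopping rules in 12.1.2 (severe allergic reaction or arterial vasospasm within 24 hours, new venous thrombosis within 3 days) run from any administration. They stop one subject's dosing and do not hold enrolment. A venous thrombosis after dose 2 that qualified as a SUSAR would end that subject's treatment while new subjects could still be enrolled with no required pause.

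Human experience with this schedule is limited in the documents. Phase 1 gave two doses about a week apart, at up to 100 million cells per treatment, and is described as safe and well tolerated. Section 11.1 reports no drug-related adverse events at half a log above this study's top dose. Neither statement covers a third dose or monthly repetition. Section 4.2 rests the schedule on animal studies, and the Introduction describes the human monthly-dosing study as ongoing and blinded. What is at stake is whether people not yet enrolled are enrolled before the DMC has looked at a new serious reaction.

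**Working it through.** The plan states no figure to reproduce here beyond the 14-day length. The check is calendar arithmetic.

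**Inputs**
- Dosing on Days 1, 29 and 57 (section 8.2), each visit ±3 days (Table of Events).
- Trigger length of 14 days from the initial dose (6.5.1 and 12.1.1).
- Month 3 visit on Day 93 ±7 days, and last visit on Day 425 (Table of Events).
- Planned size of 24 subjects (section 7.1).

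**Can the trigger ever reach dose 2?**
- Nominal end of the trigger: 1 + 14 = Day 15, which is 14 days before dose 2 and 42 days before dose 3.
- Latest end, with dose 1 given late: 1 + 3 + 14 = Day 18.
- Earliest dose 2: 29 − 3 = Day 26.
- Day 18 is before Day 26, so within the permitted windows doses 2 and 3 are never covered.

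**Share of the post-dose windows covered**
- Three doses × 14 days = 42 days.
- Covered now: 14/42 = 33%, one window of three.
- Covered if the trigger followed every dose: 42/42, nominally Days 1–15, 29–43 and 57–71.

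**Is enrolment expected to be open when the uncovered windows occur?**
- Latest end of the dose 3 window: 57 + 3 + 14 = Day 74.
- Earliest Month 3 visit: 93 − 7 = Day 86.
- Subjects dosed on schedule who have completed Month 3 have therefore passed both uncovered windows. At the two scheduled reviews that is about 0.25 × 24 = 6 and 0.50 × 24 = 12 subjects, with enrolment still expected to be open.

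This last step shows only that the uncovered windows and open enrolment overlap in time. It does not give the number of people a hold would affect, because the documents do not say how many would already be enrolled at that point.

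**Which events fall in the gap?** The allergic-reaction and malignancy triggers have no first-dose limit and so apply after any dose. What remains is a SUSAR after dose 2 or 3 that is neither of these.

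**The case against.** The strongest reply is that this is a deliberate line, drawn the same way in two sections, with real safeguards behind it. The DMC is unblinded and is obliged to evaluate all serious adverse events on an ongoing basis; only its recommendation is discretionary. It can meet ad hoc. Serious adverse events reach the sponsor within 24 hours, the sponsor's drug safety staff are unblinded, SUSARs after any dose are expedited and passed to investigators, and the sponsor may stop the study. All of this stands. A reader might infer that SUSARs after dose 2 or 3 go unmonitored; the documents do not support that. None of these provisions, however, itself suspends enrolment.

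A second reply is that the 14-day length is itself a judgement. From Day 1 to Day 425 is 424 days, so even after the change 424 − 42 = 382 days (90%) stay under DMC discretion. That is true, and the proposal does not dispute the length. It applies the sponsor's own length to each dose.

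A third is that the remedy fits a repeat-dose hazard poorly. Those closest to it are enrolled subjects awaiting their next dose, and the change does not pause their treatment. A new subject would not reach dose 2 until at least 22 days after dose 1 (Day 4 to Day 26), which leaves time for an ad hoc review. This stands for a hazard that arises only with repetition. It has less force where a reaction seen after dose 2 could equally follow a first dose.

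Finally, sections 4.1, 6.5.1 and 12.1.1 defer details to the DMC charter, which may contain further triggers. That is possible, but it would not change what 12.1.1 says.

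**Conclusion.** The point holds as a limited gap in a safety rule. Followed exactly, the trigger covers 14 of the 42 days in the three post-dose windows, and a SUSAR after dose 2 or 3 outside the other two categories does not cause the 12.1.1 suspension and ad hoc review. The missing element is the automatic pause and nothing more. It is worth correcting because correction is cheap and no reason for the limit is given.

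Two stronger readings should be resisted. A reader might infer that 6.5.1 and 12.1.1 contradict each other on the trigger. They do not: the trigger list is the same in both, and the first-dose limit is a design choice. They differ only in consequence, and the automatic hold comes from 12.1.1 alone. A reader might also turn the uncovered days into a risk, or into a number of subjects harmed or spared. The documents give no SUSAR rate and no enrolment curve, so no probability and no number of subjects affected is claimed.

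The conclusion assumes dosing within the stated visit windows, reads the initial dose as the Day 1 administration, and rests on the protocol text without sight of the DMC charter.

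**What to change.** In both 6.5.1 and 12.1.1, make the SUSAR trigger run for 14 days after any dose of product in place of the initial dose. In the same sentence, delete the trailing words that spell out the SUSAR abbreviation a second time and garble the criterion. Check the DMC charter and bring it into line. The 12.1.1 edit supplies the automatic suspension; the 6.5.1 edit keeps the two lists the same, and the chairman's role there is unchanged.

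The cost is one amended phrase in two sections, a charter check, and possibly one or more short extra enrolment holds. No new reporting process is needed, because SUSARs are already identified and expedited after any dose. The benefit is confined to people not yet enrolled. If the sponsor also wants to pause dose 2 or 3 in enrolled subjects after such an event, that needs a separate rule. A SUSAR more than 14 days after a dose would remain a matter for DMC judgement, as it is now.

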7. STUDY POPULATION

7.1. Number of Subjects and Sites

Approximately 24 subjects with diabetic peripheral neuropathy will be enrolled at about 5 sites in the United States.

7.2. Inclusion Criteria

Subjects must satisfy the following criteria to be enrolled in the study

- 1. Males and females who are at least 18 years of age at the time of signing the informed consent document.
- 2. Subject must understand and voluntarily sign an informed consent document prior to any study related assessments/procedures are conducted.
- 3. Subject is willing and able to adhere to the study visit schedule and other protocol requirements
- 4. Diabetes mellitus (DM) Type 2 as defined by the ADA or WHO criteria (Appendix A).
- 5. Meet established criteria for DPN due to Type 2 diabetes with the following:
 - a. Abnormal symptoms (NTSS-6 \ge 6 points (total score) or \ge 2.0 points for one or more symptoms)

AND

- b. Abnormal signs (UENS score of 2-24 and/or NIS-LL score of 2-10).
- 6. A female of childbearing potential must have a negative serum pregnancy test at screening and a negative urine pregnancy test prior to treatment with study therapy. In addition, sexually active Females of Child Bearing Potential (FCBP) must agree to use 2 of the following adequate forms of contraception methods simultaneously such as: oral, injectable, or implantable hormonal contraception, tubal ligation, IUD, barrier contraceptive with spermicide or vasectomized partner for the duration of the study.
- 7. Males (including those who have had a vasectomy) must agree to use barrier contraception (latex condoms) when engaging in sexual activity with FCBP for the duration of the study.

